#### **4.1.2.5. Duration of response (DOR)**

Duration of response (DOR): It is defined as the time from the date of first recorded tumor response (RECIST v1.1 or mRECIST) to the date of first recorded tumor objective progression (RECIST v1.1 or mRECIST) or the date of death due to any cause, whichever occurs first, in subjects whose BOR is CR and PR.

Censoring rules:

- If there is no baseline tumor measurement or there is baseline tumor measurement with absence of post-baseline tumor evaluation, censoring will be based on the date of first administration.
- If the subject does not have PD or die prior to the termination of the study/cut-off date for analyses or dropout and is not using a new anti-cancer drug prior to PD or death, censoring will be based on the date of the last valid efficacy evaluation.
- If a new anti-cancer treatment has been initiated before PD or death, censoring will be based on the date of the last valid efficacy evaluation prior to the new anti-cancer treatment.
- For death or progression with the absence of two or more planned visits (two visits are planned to be conducted at 26 weeks after 12 cycles of first administration and at 18 weeks prior to 12 cycles), censoring will be based on the date of the last valid efficacy evaluation prior to death or progression.
- For death or PD with the absence of two planned visits after first administration, censoring will be based on the date of first administration.

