7.1.2. Efficacy evaluation

To evaluate the primary and secondary efficacy endpoints of SHR-1210 in combination with apatinib mesylate in patients with advanced hepatocellular carcinoma as per RECIST v1.1 (Appendix II).

Baseline lesions will be assessed once every 2 cycles during the first 12 treatment cycles (bone scan will be performed if bone progression is suspected or CR is confirmed) and then once every 3 cycles thereafter. Tumor assessments are not affected by treatment discontinuation or delay. Tumor assessments may also be performed if new lesions are suspected. The first PR/CR must be confirmed after 4 weeks \pm 7 days. As per RECIST 1.1, imaging confirmation is required 4-6 weeks after the first documentation of disease progression (except those with rapid progression or significant clinical progression).

For the record and assessment of survival, the subjects will be followed up by telephone for survival once every month after leaving the group until death, lost to follow-up, withdrawal of informed consent, or termination of the study by Hengrui.

Assessments of tumor response include all known or suspected lesions.

Radiographic examination includes CT or MRI scans of the chest, abdomen, or pelvis. Brain CT or MRI is performed for subjects with known or suspected brain metastasis, while bone scan is performed for subjects with known or suspected bone metastasis (**See 7.1 Imaging Examinations for details**).

If discontinuation is indicated by deterioration of overall health in absence of objective evidence of disease progression, such event shall be reported as symptomatic deterioration.

If a subject has not undergone imaging examinations within 4 weeks prior to the end of the study, the subject should undergo an imaging examination for response assessment at the end of the study treatment or upon withdrawal from the study. For subjects with PD demonstrated by non-imaging evidence (intolerability, other conditions), a tumor evaluation is carried out every 3 months until PD, death, or the initiation of other anti-tumor treatments.

Secondary efficacy endpoints in this study include ORR, PFS, DOR, and DCR assessed by the Independent Review Committee (IRC) in accordance with the mRECIST criteria.⁷

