#### **5.4.2.5. Duration of response (DOR)**

See Section 4.1.2.5 for the definition of duration of response (DOR).

Secondary endpoint DOR is calculated in months by using the following formula: (DOR event date/censoring date - date of first response + 1) / 30.4375.

DOR is analyzed only in subjects who have the best overall response of tumor response after treatment. The ending date of response must be consistent with the date of PD of PFS or death.

Kaplan-Meier method is used to calculate the median DOR in each treated population.

Brookmeyer-Crowley method is used to estimate the two-sided 95% CI of median time, and the survival curve is drawn. The 6/9/12-month DOR rates are estimated by Kaplan-Meier method, and the corresponding 95% CIs are calculated using the log-log transformation according to normal distribution approximation with back transformation to CIs on the untransformed scale.

The response date is the date of the first observed response.

In addition, descriptive statistics such as the number of subjects, minimum, maximum, and quartile (Q1 and Q3) are used to summarize the DOR data. If the maximum values are the censoring data, they will be displayed in the form of "xx+". The number and percentage of subjects with DOR of at least 6/9/12 months are calculated. At the same time, the number and percentage of DOR events as well as the censoring number and percentage are calculated and classified according to the reason of censoring.

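### The last DOR censoring bullet in SAP 4.1.2.5 censors at first administration, before DOR begins; it fits no responder on its likely meaning and gives a negative duration on its literal one

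*SAP*

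**What the plan says.** SAP 4.1.2.5 defines DOR from the first recorded response to first objective progression or death, in subjects whose best overall response is CR or PR. SAP 5.4.2.5 repeats the restriction: "DOR is analyzed only in subjects who have the best overall response of tumor response after treatment". It computes months as "DOR event date/censoring date - date of first response + 1) / 30.4375" (the opening bracket falls outside the quote), with no floor and no exception.

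Three of the five censoring bullets in SAP 4.1.2.5 matter here:

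- First bullet: if there is no baseline measurement, or "there is baseline tumor measurement with absence of post-baseline tumor evaluation, censoring will be based on the date of first administration".
- Fourth bullet: for death or progression with two or more planned visits absent, "censoring will be based on the date of the last valid efficacy evaluation prior to death or progression". The bullet gives the gap lengths in brackets: "two visits are planned to be conducted at 26 weeks after 12 cycles of first administration and at 18 weeks prior to 12 cycles".
- Last bullet: "For death or PD with the absence of two planned visits after first administration, censoring will be based on the date of first administration".

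The last bullet is word for word the last PFS bullet in SAP 4.1.2.6, and the first is nearly the same as its PFS counterpart. Protocol 7.1.1 censors DOR only at the last evaluable tumor assessment, or at the last assessment before new anti-tumor therapy. It has no first-dose rule for DOR.

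**The concern.** PFS and TTP run from first administration, so censoring there gives a valid time of one day. DOR runs from first response, so a censoring date at first administration lies before the clock starts. The last bullet does not say that the missed visits must be the first two, that no valid evaluation may precede the event, or that the gap must come before or after response. A programmer has to supply that limit.

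If the literal wording were applied, a responder's progression or death would be replaced by a censored time that cannot validly enter a Kaplan-Meier estimate. The outputs at stake are those in SAP 5.4.2.5: median DOR, the 6/9/12-month DOR rates, the minimum and quartiles, and the counts of events and censoring reasons. DOR is estimated in responders only, so each subject weighs more than in the full analysis set.

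**Working it through.** **Inputs.** Time origin, population and formula: SAP 4.1.2.5 and 5.4.2.5. First administration is Day 1: SAP 5.1.2. Scan schedule, from Protocol 7.1.2: "Baseline lesions will be assessed once every 2 cycles during the first 12 treatment cycles", then every 3 cycles, with 4-week cycles, so every 8 and then every 12 weeks. Scan window of plus or minus 7 days: Protocol 6.2. Confirmation 4 weeks after first CR/PR: SAP 4.1.1.

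**The plan's own figures.** A gap of two missed visits is two scan intervals plus a week of window at each end:

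- before 12 cycles: 2 × 8 + 2 = 18 weeks (SAP: 18);
- after 12 cycles: 2 × 12 + 2 = 26 weeks (SAP: 26).

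Both reproduce exactly, so the SAP's missed-visit rule rests on the 8- and 12-week schedule.

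**Formula.** DOR = (event or censoring date − first response date + 1) / 30.4375 months. Scan days are assumed to fall exactly on the grid, so week w is Day 7w + 1. With censoring at Day 1:

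- response at week 8 (Day 57): (1 − 57 + 1)/30.4375 = −1.81 months;
- response at week 24 (Day 169): (1 − 169 + 1)/30.4375 = −5.49 months.

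Any response after Day 2 gives a negative value.

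**Which bullets can reach a responder?**

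- *First bullet.* A responder has a baseline and at least one post-baseline evaluation, and confirmation adds another. The bullet is dead text for DOR.
- *Last bullet, narrow reading* (first two visits missed, no valid scan before progression or death). No confirmed responder meets it.
- *Last bullet, literal reading* (two planned visits missed at some point after first administration, then progression or death). Responders can meet it, as two hypothetical patterns show.

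**Pattern A.** PR at week 8 (Day 57), confirmed at week 12 (Day 85), weeks 16 and 24 missed, PD at week 32. The gap from the last valid scan to PD is 32 − 12 = 20 weeks, beyond the 18-week limit, so the fourth bullet applies as well.

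- Fourth bullet: (85 − 57 + 1)/30.4375 = +0.95 months, censored.
- Last bullet: −1.81 months, censored.

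The SAP does not say which prevails.

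**Pattern B.** Weeks 8 and 16 missed, PR at week 24 (Day 169), confirmed at week 28, scan at week 32, PD at week 40 (Day 281). The gap before PD is 8 weeks, so the fourth bullet does not apply.

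- No missed-visit censoring: (281 − 169 + 1)/30.4375 = +3.71 months, an event.
- Last bullet, read literally: −5.49 months, censored.

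**After the fix.** Pattern A is censored at +0.95 months and pattern B is an event at +3.71 months. Censoring on or after first response cannot give less than 1/30.4375 = 0.03 months.

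**The case against.** The strongest answer is that the last two bullets work as a pair. The fourth covers progression or death after missed visits when a valid evaluation exists to censor at; the last covers the case where the first two visits were missed and first administration is the only date available. The TTP bullet in SAP 4.1.2.4 supports this order, since it speaks of progression after the absence of the visits. In pattern B valid scans lie between the missed visits and the progression. The literal reading would also censor that patient's PFS at Day 1 despite those scans, which is a good reason to doubt that it was intended. SAP 5.4.2.5 also requires the end of response to agree with the PFS progression date or death, which explains the parallel rules and weighs against dropping a progression that PFS counts.

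Most of this stands. The narrow reading is the natural one, and under it no negative DOR arises. But it then leaves the bullet with nothing to do in DOR, and the text does not state the limit on which that reading depends. The consistency sentence does not settle the order of the two bullets either, because PFS carries the same pair.

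A reader might go further and infer that the DOR rules in general produce negative durations, or that the median DOR is distorted. The documents do not support that. The first bullet cannot reach a responder, the last does so only on its literal wording in uncommon missed-visit patterns, and nothing in the documents shows how many responders would have such a pattern or how the software would treat a negative time.

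**Conclusion.** The point holds in limited form. The last bullet of SAP 4.1.2.5 is inapplicable to DOR on its likely meaning and gives an impossible value on its literal one. On the literal reading it can also conflict with the fourth bullet, with no stated precedence, and its censoring date departs from Protocol 7.1.1. The first bullet is merely redundant.

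Where the literal rule is applied, the error is large for the individual patient: −1.81 against +0.95 months in pattern A, and −5.49 against an event at +3.71 in pattern B. These values assume scans on the nominal 8-week grid and hypothetical visit histories. Across the trial the effect is probably small: few patients, and one descriptive secondary endpoint. The decision rules in SAP section 3 rest on ORR, so no efficacy conclusion depends on this. It is a minor correction.

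**What to change.** In SAP 4.1.2.5:

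1. Delete the last bullet, and the first bullet as inapplicable.
2. In the fourth bullet, state that for DOR two or more missed planned visits are counted only after first response.
3. State that the censoring date is the last valid evaluation on or after first response. If no later valid scan exists, this is the response date itself, so no separate rule is needed.

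This brings the censoring date into line with the last-assessment censoring in Protocol 7.1.1. The protocol has no missed-visit rule for DOR, so the fourth bullet remains a SAP addition and can be labelled as such. The cost is two deletions and two clarifying statements in the SAP, with the matching change to the DOR derivation. It needs no new data and does not affect the sample size or the ORR analysis.

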**4.1.2.6. Progression-free survival (PFS)**

Progression-free survival (PFS): It is defined as the time from the date of first administration to the date of first recorded tumor progression (assessed as per RECIST v1.1 or mRECIST) or the date of death due to any cause, whichever occurs first.

Censoring rules:

- If there is no baseline tumor measurement or there is baseline tumor evaluation but with missing tumor evaluation after baseline, censoring will be based on the date of first administration.
- If the subject does not have PD or die prior to the termination of the study/cut-off date for analyses or dropout and is not using a new anti-cancer drug prior to PD or death, censoring will be based on the date of the last valid efficacy evaluation.
- If a new anti-cancer treatment has been initiated before PD or death, censoring will be based on the date of the last valid efficacy evaluation prior to the new anti-cancer treatment.

- For death or progression with the absence of two or more planned visits (two visits are planned to be conducted at 26 weeks after 12 cycles of first administration and at 18 weeks prior to 12 cycles), censoring will be based on the date of the last valid efficacy evaluation prior to death or progression.
- For death or PD with the absence of two planned visits after first administration, censoring will be based on the date of first administration.

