Apatinib administration ^[20]			Oral administration once a day after meal						
Apatinib dispensing/retrieval ^[21]			×		×		×		
Imaging Evaluation									
Imaging examination ^[22]	×		Once every 2 cycles in the first 12 cycles of dosing, followed by once every 3 cycles				×		
Follow-Ups After Discontinuation									
Time to progression ^[23]							Imaging evaluations are performed once every 3 months (± 7 d) until disease progression or start of new anti-tumor treatments (for subjects with non-radiological PD)		
Death ^[24]									×
Blood Sampling and Tumor Tissue Sampling									
Blood/tissue sampling for biomarkers ^[26]	×								

Notes:

- [1] Tumor history/past medical history: tumor diagnosis, surgical history, interventional therapy, local ablation therapy, systemic treatment, radiation therapy, as well as past treatments of other conditions, history of cancers other than HCC.
- [2] Concomitant medications and treatments received within 30 days prior to the first dose and during the study period should be recorded. Once a subject discontinues the investigational treatment, only concomitant medication or treatment for new or unresolved treatment-related adverse events are recorded, until 30 days after the last dose.
- [3] Routine blood test: WBC, neutrophils, lymphocytes, RBC, hemoglobin, and platelets. Performed within 7 days prior to enrollment, on Day 15 of Cycle 1, Day 1 and 15 of subsequent cycles, at the end of study, and 30 days after the end of treatment.
- [4] Blood biochemistry: total bilirubin, direct bilirubin, ALT, AST, AKP, γ -GT, total protein, albumin, urea/blood urea nitrogen, creatinine, uric acid, fasting blood glucose, TG, cholesterol, potassium, sodium, chlorine, calcium, phosphorus, blood lipase (only during the screening period and in case of subsequent abdominal pain, abdominal distension and other symptoms of suspected pancreatitis), blood amylase (only during the screening period and subsequent abdominal pain, abdominal distension and other symptoms of suspected pancreatitis). It is carried out within 7 days before enrollment, on Day 15 of Cycle 1, Day 1 and Day 15 of subsequent cycles, at the end of study, and 30 days after the treatment.

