7. EVALUATIONS

7.1. Efficacy Evaluation

7.1.1. Efficacy indicators

The primary efficacy endpoint for this study is the objective response rate (ORR) as assessed by independent review committee (IRC) as per RECIST 1.1.

Objective response rate (ORR): The proportion of subjects with a best overall response (BOR) of complete response (CR) or partial response (PR) as per RECIST 1.1 criteria.

CR and PR must be verified at least 4 weeks \pm 7 days after their first presence.

Best overall response refers to the best response assessed by the IRC, or the best response from the date of first dose to the first documentation of progression as per RECIST 1.1 or to the start of a new anti-tumor treatment (whichever comes first).

For subjects without documented progression or new anti-tumor treatment, the best overall response will be determined on the basis of all efficacy assessments.

For subjects who continue SHR-1210 treatment beyond progression, the best overall response should be based on the efficacy assessment at the time of first documented progression as per RECIST 1.1.

Secondary efficacy endpoints include:

- Objective response rate as assessed by the investigator as per RECIST 1.1;
- Progression-free survival (PFS): The period of time from the date of first dose to the date of the first recorded tumor progression (according to RECIST v1.1 criteria, regardless of whether treatment is continued) or death of any cause (whichever comes first).

When determining PFS, clinical exacerbations without definite evidence of disease progression (as per RECIST 1.1) is not considered progression. For subjects who die without any prior reports of progression, the date of death is considered the date of progression. Subjects without disease progression or death will be censored on the date of their last evaluable tumor assessment. Subjects without tumor assessments during the study or death will be censored on their date of first dose. Subjects who discontinue the treatment for reasons other than disease progression (no subsequent tumor assessments) will be censored on the date of their last evaluable tumor assessment. Subjects without disease progression before starting a new anti-tumor therapy will be censored on the date of their last evaluable tumor assessment prior to the start of new anti-tumor therapy.

- Time to objective response (TTR) is defined as the period of time from the date of first dose to the first documented tumor response (as per RECIST 1.1).

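### The SAP's PFS rules censor at first dose subjects who die without a post-baseline scan, whereas the protocol counts those deaths as events; applied literally, this raises the PFS estimate

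*SAP*

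**What the plan says.** SAP 4.1.2.6 defines PFS as running from first dose to progression "or the date of death due to any cause, whichever occurs first". Five censoring bullets follow, and three matter here.

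- First bullet: where "there is baseline tumor evaluation but with missing tumor evaluation after baseline, censoring will be based on the date of first administration". Death is not mentioned.
- Second bullet: it does carry a condition on death, since it opens "If the subject does not have PD or die prior to the termination of the study/cut-off date for analyses or dropout".
- Last bullet: "For death or PD with the absence of two planned visits after first administration, censoring will be based on the date of first administration".

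Protocol 7.1.1 reads differently: "For subjects who die without any prior reports of progression, the date of death is considered the date of progression", and "Subjects without tumor assessments during the study or death will be censored on their date of first dose". The natural reading is that first-dose censoring needs both conditions, no assessment and no death. The protocol has no missed-visit rule for PFS.

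The SAP's missed-visit bullet explains its window in a parenthesis: "two visits are planned to be conducted at 26 weeks after 12 cycles of first administration and at 18 weeks prior to 12 cycles". The protocol's Procedures of the Trial table sets a different scan schedule for subjects who stop treatment without radiological progression: "Imaging evaluations are performed once every 3 months (± 7 d) until disease progression or start of new anti-tumor treatments".

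**The concern.** The SAP states that it is drafted from protocol version 3.0 and declares no departure on PFS, yet the two documents treat an unscanned early death in opposite ways. Such a death is an event under the protocol. Under the literal SAP text it leaves the risk set on day 1 and contributes nothing to the curve.

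These subjects have the worst outcomes, so the censoring is informative and pushes the estimate up. The trial has a single arm, so PFS will be read against outside figures and no control arm shares the distortion. Two programmers, one working from each document, could report different medians and 6/9/12-month PFS rates from the same data.

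The missed-visit window raises a smaller, related question. It appears to be built on the on-treatment scan interval only.

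**Working it through.** **1. The plan's own figures.** The documents give no PFS assumption, event count or power. The figures that can be reproduced are the missed-visit windows. Scans fall every 2 cycles of 4 weeks (8 weeks) for the first 12 cycles and every 3 cycles (12 weeks) thereafter, each ±7 days (Protocol 6.2 and 7.1.2). Then 2×8 + 2×1 = 18 weeks and 2×12 + 2×1 = 26 weeks. Both match the SAP. The first scheduled scan is at week 8.

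**2. One subject under each rule.** Take a death on study day 35 with no post-baseline scan and no new anti-cancer treatment.

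- Protocol 7.1.1: event at 35/30.4375 = 1.15 months.
- SAP first bullet: censored at first dose, at 1/30.4375 = 0.03 months.

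No other SAP bullet restores the death as an event. The last bullet sends a later unscanned death, after two missed visits, to the same day-1 censoring.

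**3. Effect on the curve.** PFS is analysed in the FAS by Kaplan-Meier (SAP 5.4 and 5.4.2.2). Let a fraction f die before any scan, all by week 8, and let S_rest(t) be the PFS of the others.

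- Protocol rule: S(t) = (1−f) × S_rest(t) for t from week 8 onward.
- Literal SAP rule: the f are gone at day 1, so the curve estimates S_rest(t) = S(t)/(1−f).

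The ratio of SAP to protocol is 1/(1−f): 1.020, 1.053, 1.087 and 1.136 at f = 2%, 5%, 8% and 12%.

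**4. Effect on the median.** If protocol-rule PFS is exponential with median m, the SAP median solves S(t) = 0.5(1−f), so it equals m × log2(2/(1−f)).

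| f | log2(2/(1−f)) | m = 5.5 months (assumed) becomes |
|---|---|---|
| 3% | 1.044 | 5.7 |
| 5% | 1.074 | 5.9 |
| 8% | 1.120 | 6.2 |
| 12% | 1.184 | 6.5 |

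If the exponential form is placed on the SAP-rule curve instead, the overstatement is m/(m × log2(2(1−f))), or about 8%, 14% and 23% at f = 5%, 8% and 12%. The size therefore depends somewhat on the assumed shape.

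**5. Check by simulation.** With n = 120, 2,000 runs, f = 8% and an exponential median of 5.5 months in the others, 6-month PFS averaged 46.9% under the SAP rule and 43.2% under the protocol rule. The identity gives 46.9% × 0.92 = 43.1%, which agrees to rounding.

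**6. A range for f (assumption).** Week 8 is 56/30.4375 = 1.84 months. Under a constant hazard, the survival figures in Protocol 1.1 give:

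- 12-month survival 73% (nivolumab, no prior sorafenib): 1 − 0.73^(1.84/12) = 4.7%
- 12-month survival 58% (nivolumab, prior sorafenib): 1 − 0.58^(1.84/12) = 8.0%
- median OS 9.71 months (apatinib alone, 850 mg): 1 − 0.5^(1.84/9.71) = 12.3%

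For scale, 8.0% of 120 is about 10 subjects and 4.7% of 56 is about 3.

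**7. Off-treatment window.** Taking 3 months as 13 weeks, one missed scan leaves 2×13 = 26 weeks to the next scheduled scan, or 24 to 28 weeks with ±1 week at each end. All of these exceed 18 weeks. If the parenthesis is programmed as a fixed-week test, one missed off-treatment scan would be handled as two.

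**The case against.** The best defence is that the SAP's bullets should be read together. The PFS definition counts any death, and the mention of death in the last bullet would be redundant if the first bullet already covered every unscanned death. The drafters may therefore have meant an unscanned death before two missed visits to be an event. That makes the intent unclear, but it does not rescue the rule. No bullet says so, and the last bullet still censors later unscanned deaths at first dose, against Protocol 7.1.1.

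Several limits stand.

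- The bias is conditional. A reader might infer that reported PFS is certainly inflated, but with no unscanned deaths the effect is zero.
- The 5–12% range leans high. Entry requires expected survival of at least 12 weeks, Child-Pugh class A and ECOG 0–1. Unscheduled and end-of-treatment scans mean that some early deaths would follow an assessment.
- Not all the informative censoring comes from the SAP. Protocol 7.1.1 itself censors at the last evaluable scan subjects who stop for reasons other than progression and are not scanned again, and subjects who start new therapy before progression.
- The distortion would be visible. SAP 5.4.2.2 reports PFS censoring by reason, and OS in the same analysis set counts every early death.

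On the window, the SAP's trigger is worded as two or more planned visits, so the 18-week figure bites only if it is programmed as a fixed-week test. Even then, a death or an unscheduled scan can come sooner: with a scan missed at week 13 and death at week 16, the gap is 16 weeks, inside the window.

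**Conclusion.** The conflict between SAP 4.1.2.6 and Protocol 7.1.1 is real. Followed literally, the SAP rule moves PFS in the favourable direction whenever there are unscanned deaths that the protocol would count. The factor on every PFS rate from week 8 onward is 1/(1−f). The median rises by about 4%, 7%, 12% and 18% at f = 3%, 5%, 8% and 12% if protocol-rule PFS is exponential. The documents do not give f; the 5–12% range rests on background survival from other treatments and a constant hazard, and is probably an upper range.

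This should be fixed, but it is not critical. PFS is a secondary endpoint with no decision rule. The ORR criterion is untouched, because unscanned subjects stay in the FAS denominator as non-responders.

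Two stronger inferences are not supported.

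- A reader might conclude that the 18-week window wrongly censors a fully compliant off-treatment subject. The longest compliant gap is 4 weeks + 13 weeks + 1 week = 18 weeks, which reaches the window without exceeding it, and that subject has missed no visit.
- A reader might also conclude that the same no-scan wording in the DOR rules yields negative durations. DOR is restricted to subjects with a best response of CR or PR, who necessarily have post-baseline scans, so that bullet cannot apply to them.

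**What to change.** In SAP 4.1.2.6:

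- Add to the first bullet the condition *and the subject has not died*, and state that a death with no post-baseline scan and no prior new anti-cancer treatment is a PFS event on the date of death.
- Reconcile the last bullet with Protocol 7.1.1, so that both documents say whether an unscanned death after two missed visits is an event.
- Define the missed-visit window by the schedule the subject is on: 18 or 26 weeks on treatment, and 2×13 + 2×1 = 28 weeks in 3-monthly off-treatment follow-up.
- Report the number of deaths without a post-baseline scan, and give PFS under the alternative rule as a sensitivity analysis.

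The cost is SAP wording and a small programming change. No new data are needed. If there are unscanned deaths, PFS becomes slightly less favourable.
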